2.7.3 Recruitment extension

Various issues caused delays in establishing the study at many participating sites, with the supply of mesh, delay in establishing research nurse support and the waiting time for surgery being the main issues. Therefore an extension to the recruitment phase of the trial is necessary to achieve the required recruitment targets.

1. Primary repair RCT

At steady state, the recruitment rate was assumed to be approximately 84 primary repair women per month. However recruitment to the primary repair trial has been slower than anticipated.

The revised projections for the extension period are based on a moving average from the previous two months (October and November 2011), resulting in an expected mean recruitment figure of 70 primary repair women per month (1.9 women per centre per month). Allowing for a staggered start for the remaining centres (37 in total), a 12 month extension will be required to reach the originally specified sample size.

2. Secondary repair RCT

It was estimated that 30% of the women screened during PROSPECT would be having a secondary or subsequent repair. Therefore, during the proposed time period for randomising 1450 women to the primary repair trial, it was anticipated that approximately 620 women having secondary surgery would also be randomised. However recruitment to the secondary repair arm has been lower than expected. The main reason for this is that a secondary repair in PROSPECT is defined as a

recurrence of prolapse after a previous procedure, when the recurrence is in the **same** compartment. An analysis of the first 1000 women recruited to PROSPECT indicated that approximately 16% of women meet this criterion. As a result there are fewer women than expected who are eligible for the secondary repair trial (16% compared with the anticipated 30%).

Although a 12 month extension will not be sufficient in terms of achieving the original recruitment target for this RCT, it is anticipated that 174 women will be randomised.

3 TRIAL INTERVENTIONS (Operations and Standard Operating procedures)

3.1 Planned interventions

Women will be randomised to an operation (see Appendix I, Section 1.3) according to their surgical history (previous prolapse repair or not), the availability of the mesh (non-absorbable and/or biological) and the skill capacity of their operating gynaecologist (trained in mesh kit use or not). The study design is shown in the Flow Diagram (Appendix II).

If the non-absorbable mesh inlay or the biological mesh graft is temporarily or permanently (due to financial constraints) unavailable then the women can be randomised to one of the other two arms.

In addition, the expectation is that mesh kits would normally only be used for women who had been randomised to this option. If the operating gynaecologist is not trained in the use of mesh kits the women under their care will be randomised to one of the other two arms. Furthermore, in view of the scarcity of data about its safety and efficacy, we propose to use it only for women who are having a secondary procedure, who have a more complex prolapse problem.

Therefore, women having a primary repair may be randomised to:

- standard anterior and/or posterior repair (central plication) (reference technique);
- standard anterior and/or posterior repair with biological mesh inlay; or
- standard anterior and/or posterior repair with a non-absorbable or hybrid mesh inlay.

Women having a secondary repair may be randomised to:

- standard anterior and/or posterior repair (central plication) (reference technique);
- standard anterior and/or posterior repair with a non-absorbable or hybrid mesh inlay: or
- a mesh kit (using an introducer device) with a non-absorbable or hybrid mesh.

As different mesh types and materials are being introduced, surgeon preference, ability and availability may influence the technologies chosen. However, choices will be limited to mesh from two classes: biological mesh (primary surgery only) or non-absorbable / hybrid mesh. Mesh type and divergence from pre-specified choices will be documented with reasons. All other operative variables will be recorded or standardised using agreed protocols.

The exact operative protocols, including permitted types of mesh, will be agreed and standardised by consensus with the Research Committee of BSUG before the trial begins.

Control interventions

The women in different arms of the surgical trials will act as controls for each other (within each trial). However, the first option (standard anterior and/or posterior

repair) will be regarded as the reference technique for each of the randomised alternatives.

4 SUBSEQUENT ARRANGEMENTS

4.1 Informing key people

Following formal trial entry:

The Study Office will:

i) inform the woman's General Practitioner (by letter enclosing information about PROSPECT and Study Office contact details.

The local Recruitment Officer will:

- i) file the Hospital Copy of the Consent form in the hospital notes along with information about PROSPECT and the POP-Q measurements.
- ii) inform the ward and theatre staff as appropriate of the woman's entry to the study and details of the intervention allocation (theatre only).
- iii) use the PROSPECT internet database to enter data regarding the participant, including data required to complete randomisation; and intra-operative and postoperative information abstracted from local medical records.
- iii) return all study documentation to the Study Office in Aberdeen after database entry of essential data.

4.2 Monitoring the women

Women will be contacted by phone, post or email as appropriate. In case of non-return of questionnaires, or non-attendance at outpatient appointments, attempts will be made by staff at the Study Office to trace the women directly using these means or indirectly by contacting the GP or the Best Contact.

Notification by GPs

GPs are asked to contact the Study Office if one of the participants moves, becomes too ill to continue or dies, or any other notifiable event or possible serious adverse event occurs. Alternatively, staff at the Study Office may contact the GP.

Notification by 'Best Contact'

If the PROSPECT Study Office loses touch with a participant (eg questionnaires), we will try to establish why via the 'Best Contact'. Women will be asked when they join the study to nominate a family member or close friend, who will be asked to agree to this nomination.

Offices for National Statistics (HES data in England, ISD data in Scotland)

Consent will be sought from all women to trace their medical records and addresses from centrally held computerised databases. This should facilitate longterm follow up.

5. DATA COLLECTION AND PROCESSING

Follow up will continue for 24 months from the date of operation. It is not part of this protocol or the current study to follow up the women beyond this time. However, consent will be sought to make this possible in the future, and long term follow up is planned (Appendix IV).

5.1 Questionnaires

Women will be asked to complete a baseline questionnaire before surgery. Follow up questionnaires will be sent by post at 6, 12, 18 and 24 months after surgery. Content will include:

i) Prolapse symptoms (POP-SS,⁷)

- ii) Urinary outcome questions (urinary symptoms and urinary leakage, effect on QOL, http://www.iciq.net/), pad use, catheter use)
- iii) Bowel function outcome questions and effect on QoL
- iv) Sexual function and vaginal symptoms, effect on QoL (http://www.iciq.net)
- v) Health care utilisation questions
- vi) Exercise, weight and height, including pelvic floor exercises
- vii) EQ 5D¹²

and additionally at baseline only:

- i) Obstetric history
- ii) GP address and phone number
- iii) 'Best Contact' at another address for follow up (not wife or partner)
- iv) Other medical problems
- v) Date of operation

Postoperatively within a week of surgery:

- i) infection / pyrexia
- ii) pain and pain relief
- iii) blood transfusion
- iv) vaginal pack
- v) urinary catheter and recatheterisation
- vi) bowel function (need for laxatives)
- vii) complications and return to theatre
- viii) length of stay

At 12 months after surgery (randomised women only):

ii) clinical findings

At 18 months only:

i) Participant Unit Cost Questionnaire

At 6, 12 and 24 months:

- i) Complications
- ii) Need for further treatment for prolapse
- iii) Further treatment for prolapse received or planned, use of health services

Theatre findings and procedures will be recorded in the BSUG database, using a questionnaire designed to be compatible with the requirements of both BSUG and PROSPECT.

5.2 HES and ISD Data

Approximately 24 months after the last woman has been recruited we will run a check for operations, diagnoses and hospital admissions with centrally collected data, to supplement and validate data collected from the participants, and to set up mechanisms for long-term follow up.

5.3 Data processing

Data from the various sources outlined above will be sent to the Study Office in Aberdeen for processing. Staff in the Study Office will work closely with local Recruitment Officers to ensure that the data are as complete and accurate as possible. Extensive range and consistency checks will further enhance the quality of the data.

6. ANALYSIS PLANS

6.1 Ground rules for the statistical analysis

The statistical analysis of the RCTs will be based on all women as randomised, irrespective of subsequent compliance with the treatment allocated. The principal comparisons will be:

- (A) In women having a primary prolapse repair,
- 1) a standard anterior and/or posterior repair will be compared with a standard repair using a biological graft inlay; and
- 2) a standard anterior and/or posterior repair will be compared with a standard repair using a non-absorbable or combined mesh inlay.
- (B) In women having a secondary prolapse repair,
- 3) a standard anterior and/or posterior repair will be compared with a standard repair using a non-absorbable or combined mesh inlay; and
- 4) a standard anterior and/or posterior repair will be compared with a mesh kit procedure using an introducer device.

The two trials are being considered independently because different surgical options are considered to be appropriate for clinical reasons.

Women who are not randomised but who are in the Comprehensive Cohort group will be analysed according to the operation actually carried out.

It is anticipated that the data generated by the study, along with other focused data collection sets, may be used as a basis for exploratory or epidemiological research, but these will be described in separate protocols.

6.2 Measures of outcomes

Primary outcomes

- 1. The primary patient-reported outcome is symptoms of prolapse, measured as (i) the number and frequency of prolapse symptoms on the Pelvic Organ Prolapse Symptom Scale (POP-SS), (POP-SS questions A1-A7⁷) at one year after surgery and (ii) a quality of life outcome measured as the overall effect of prolapse symptoms on everyday life.
- 2. The primary economic outcome measure of cost effectiveness is incremental cost per QALY (QALYs based on the EQ-5D⁸)

Secondary outcomes

General

- immediate and late post-operative morbidity (injury to organs, excess blood loss, blood transfusion, infection (UTI, sepsis, abscess), pain, urinary retention, constipation);
- other adverse effects or complications including mesh erosion or removal;
- operating time;
- blood loss:
- number of nights in hospital;
- time until resumption of usual activities;

Prolapse outcomes

- subjective recurrence of prolapse;
- subjective continuation / recurrence of prolapse symptoms;
- objective residual prolapse stage (POP-Q) at original site;
- development of new (de novo) prolapse at another site; and
- need for other conservative prolapse treatment (e.g. PFMT, mechanical device).
- need for further surgery for prolapse and/or for urinary incontinence;

- time to further surgery; and
- satisfaction with surgery.

Urinary outcomes

- Urinary incontinence (persistent or de novo, and types of incontinence); and
- Need for alternative management for incontinence (e.g. PFMT, mechanical devices, pads, surgery, drugs, intermittent catheterisation).

Bowel outcomes

- Constipation (persistent or de novo);
- Bowel urgency (persistent or de novo); and
- Faecal incontinence (persistent or de novo).

Vaginal symptoms and sexual function outcomes

- Vaginal symptoms; and
- Dyspareunia / apareunia / difficulty with intercourse (persistent or de novo).

Quality of life outcome measures

- Condition-specific quality of life measures (urinary, bowel, vaginal, sexual);
- General health measure (EQ-5D⁸)

Economic outcome measures

- Cost and use of NHS services;
- Cost to the women and their families/carers;
- QALYs estimated from the responses to the EQ-5D⁸;
- The incremental costs, QALYs and incremental cost per QALY derived by the economic model.

Woman-reported outcomes will be assessed by participant-completed questionnaires in hospital after surgery and at home at 6, 12, 18 and 24 months. Gynaecologists, supported by Recruitment Officers, will complete a questionnaire at the time of surgery providing details of the operative procedures, complications and resource use, and a short clinical questionnaire at the 12 month outpatient review appointment including a POP-Q measurement.

Economic outcomes will be assessed using standard economic methods plus study-specific data collection described earlier. The standardised outcome instruments developed by the International Consultation on Incontinence (ICI)⁹ for urinary and bowel function will be used. We will use the International Continence Society (ICS) recommendations for terminology and standard techniques.¹⁰ Consumer groups and our Consumer Advisor will contribute to ensuring that all relevant issues are covered, the patient information and survey instruments are acceptable to the women and the outcome measures relevant.

The ways in which these data will be analysed are set out in the PROSPECT Statistical Analysis Plan and Dummy Tabulations.

It is anticipated that the data generated by the study, along with other focused data collection sets, may be used as a basis for exploratory or epidemiological research, but these will be described in separate protocols.

6.3 Statistical analysis

A single principal analysis is anticipated at 12 months after the last woman is recruited. The Data Monitoring Committee will determine the frequency of confidential interim analyses, but at present these are planned on four occasions during the data collection period.

All analyses within the RCT will be based on the intention-to-treat principle. All outcomes in both trials will be described with the appropriate descriptive statistics where relevant: mean and standard deviation for continuous and count outcomes, or medians and inter-quartile range if required for skewed data, numbers and

percentages for dichotomous and categorical outcomes (for example subjective recurrence of prolapse).

Analysis of the primary outcome (POP-SS) will estimate the mean differences (and 95% confidence interval) between the intervention and control groups using a general linear model that adjusts for the minimisation covariates and other important prognostic covariates, including the baseline symptom score, at 12 months after surgery. A similar analysis will be used to analyse the primary outcome at 6 and 24 months.

All secondary analyses will be analysed in a similar manner but using the appropriate generalised linear model (for example logistic regression for dichotomous data such as subjective prolapse failure, Poisson or negative binomial regression for count data such as number of nights in hospital) or time to event methods (e.g. Cox regression on time to further surgery) where required. We will explore analysing outcomes at all time points simultaneously using for example, Generalised Estimating Equations or Generalised Linear Latent and Mixed Models, and relevant link functions, to explore changes in outcome over time.

Within the non-randomised women included in the Comprehensive Cohort Study, efficacy and safety outcomes will be described using the same descriptive statistics as above. Randomised and non randomised cohorts will be compared on baseline characteristics initially. An exploratory analysis will replicate the analysis of the randomised trials as stated above on the non-randomised cohort. A further exploratory analysis will assess any potential differential treatment effects between randomised and non-randomised cohorts. This will allow us to provide potentially more precise estimates of effects and to place the findings of the RCT in the context of the Comprehensive Cohort evidence, thus increasing the generalisability of findings.

Proposed frequency of analyses

Women will be followed up at 6, 12, 18 and 24 months after their prolapse operation. They will be asked to consent to long-term follow up although this is not to be funded by this application.

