- (2) A woman who is having a second or subsequent repair will be randomised to: d) a standard anterior or posterior prolapse repair, e) a standard repair with a non-absorbable mesh inlay to support the stitches, or f) a new mesh repair in which the whole prolapse is held up with a large piece of mesh threaded into surrounding tissues using an introducer (mesh kit). This last option will only be available for women having a secondary operation for prolapse as it is thought that it is a more invasive operation than the other options and so should be reserved for such women, who have a higher risk of failure.

It is likely that there will be mixed costs and benefits for these operations. For example there may be better cure rates with some operations although with a higher chance of complications especially related to mesh or at a higher cost to both the NHS and patients.

All women having prolapse operations will be eligible for our study. They will be given information about the study before they are admitted to hospital. After discussion with their gynaecologist, women will be able to choose whether or not they are willing to be randomised to one of the specified operations. They will sign a consent form approved by the Ethics Committee. Those women who do not wish to be randomised to a particular procedure but are happy for their outcomes to be monitored, will be examined and will complete the questionnaires in the same way as the randomised groups.

Women will have a routine physical examination before surgery and they will complete questionnaires both before and after their operation. Further symptom questionnaires will also be filled in 6, 12 and 24 months later. The women will be examined and reviewed in outpatients at 12 months after surgery. Our main interest is in the cure or improvement of prolapse symptoms, as reported by the women themselves. We have carried out feasibility studies using these questionnaires and examination methods to show that we will be able to measure differences.

Ethical approval has been sought for this study. We consider that it is ethical to study this problem using randomisation as this is the gold-standard method most likely to provide an unbiased answer. The procedures used in the study will be standardised and agreed with a team of experienced gynaecologists from the British Society of Urogynaecology.

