2.2 Identification and enrolment of potential participants

All women who require pelvic organ prolapse (POP) surgery will be identified by a dedicated Recruitment Officer in each centre. A log will be maintained of all women meeting the eligibility criterion (admission for prolapse surgery), describing reasons if

they do not agree to enter the study or be randomised. Every woman will be allocated a unique Study Number.

Every eligible woman will be given a flyer containing a brief summary of the study when they attend their initial clinic appointment. She will then be given the Patient Information Sheet with her admission documents (which may be during the initial clinic appointment) or by separate mail if the woman agrees. Women will have the opportunity to discuss all aspects of the study with their GP and/or family members before admission, and their gynaecologist, the Recruitment Officer, and staff at preadmission clinics and/or when admitted to hospital. In addition, all documentation will have the PROSPECT Study Office contact details to enable women to obtain information from the study organisers. Signed consent will be obtained from each woman to participate (and, if suitable, to be randomised) and followed up after her prolapse surgery by questionnaires and an examination in Gynaecology Outpatients. The Patient Information Sheet and the Consent Form both refer to the possibility of long-term follow-up, being contacted about other prolapse research and access to their NHS records for these purposes.

Women who do not wish to be randomised, or are not suitable for randomisation, will still be eligible to be followed-up using the same Study Protocol as part of the Comprehensive Cohort. They will complete all the study procedures and documents including follow-up, except for the examination at 12 months.

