All randomised participants will have a review appointment with an appropriately qualified Recruitment Officer and, if necessary, their gynaecologist, at 12 months to evaluate the results of surgery and identify problems or a need for other treatment. In some sites, this amounts to more postoperative surveillance than is available routinely in the NHS, and should ensure that women receive optimum care.

2.3 Randomisation and allocation to management group for women who consent to be randomised (avoiding selection bias)

When contact details, essential baseline information and confirmation of signed consent are entered into the internet based PROSPECT database, the local researcher will be able to randomise the woman (if appropriate) to one of the groups for which she is eligible (see Flow Diagram, Appendix II). Randomisation will be carried out as close to the time of surgery as is practical (either on the morning of the operation or the previous afternoon), taking into account the hospital routines and time needed for setting up the operating theatre.

Randomisation will utilise the existing proven remote automated computer randomisation application at the study adminstrative centre in the Centre for Healthcare Randomised Trials (CHaRT, a fully registered UK CRN clinical trials unit) in the Health Services Research Unit, University of Aberdeen. This randomisation application will be available both as a telephone-based IVR system and as an internet based service.

Randomisation will be computer-allocated and stratified depending on whether a woman is having a primary or secondary repair.

Primary prolapse (de novo) is defined as a prolapse in a compartment that has not previously been repaired. If the woman is having two primary procedures (i.e. both anterior and posterior vaginal wall prolapses require repair), the randomised allocation will be applied to both prolapse repairs.

Secondary prolapse is defined as a recurrence of prolapse after a previous procedure, when the recurrence is in the **same** compartment. If the woman also needs a concomitant primary repair of a de novo prolapse in a different compartment, this procedure will be chosen on clinical grounds (i.e. not dictated by the randomisation allocation for the secondary procedure).

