APPENDIX IV LONG TERM FOLLOW-UP

Background

PROSPECT (PROlapse Surgery, Pragmatic Evaluation by randomised Controlled Trial) is the largest randomised controlled trial conducted to date of the use of mesh in women having prolapse surgery. It addresses the use of no mesh, a biological mesh inlay, and a nonabsorbable mesh inserted as an inlay or used in a kit; and separately in women having their first prolapse operation or repeat surgery.

PROSPECT recruited 3091 women from 35 centres across the UK between January 2010 and August 2013. There were two trials, one amongst women having their first prolapse operation (Primary trial, where 1353 women were randomised to no mesh, non-absorbable mesh inlay or biological mesh inlay); and those having repeat surgery (Secondary trial, where 155 women were randomised to no mesh, non-absorbable mesh inlay or mesh kit). Women who were not eligible for randomisation were enrolled into the Comprehensive Cohort (1583 women). The following information was collected:

- Demographic and surgical information at recruitment and at operation;
- Patient reported outcome data (prolapse symptoms, urinary, bowel and sexual function and EQ-5D) through questionnaires at 6, 12 and 24 months;
- Randomised women were examined 12 months after surgery to identify treatment success and adverse effects;
- Information about complications, readmissions, reoperations and costs.

Within the main PROSPECT trial short term failure (within two years of the prolapse operation) was captured. However, as prolapse is a progressive and relapsing condition, with surgery having a high failure rate¹ (repeat surgery occurs on average 12 years later) it is essential to capture the long term failure in order to truly evaluate the potential benefits of mesh versus its adverse effects, which may also occur many years later.² In addition, there is very little information about the long term effects of this condition on urinary, bowel and sexual function,

Current evidence

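### The planned trial-versus-cohort comparison makes no exception for outcomes that depend on the 12-month examination, which only randomised women have; mesh-specific events are likely to be under-detected in the cohort and POP-Q cannot be compared

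*Protocol*

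**What the plan says.** Protocol section 6.3 plans three things for the cohort. Efficacy and safety are described with the same statistics as in the trials. Then, "An exploratory analysis will replicate the analysis of the randomised trials as stated above on the non-randomised cohort". Finally, "A further exploratory analysis will assess any potential differential treatment effects between randomised and non-randomised cohorts". The stated gains are precision and generalisability. No outcome is set aside, and the outcomes in section 6.2 include mesh erosion or removal, POP-Q stage at the original site and new prolapse at another site.

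The SAP (General Methods) says only that cohort women are analysed by the operation they received. It does not mention the replication, the comparison with the trials or how events are ascertained, although protocol section 6.4 says all study analyses will follow the SAP.

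On follow-up, section 2.2 says of cohort women: "They will complete all the study procedures and documents including follow-up, except for the examination at 12 months". Sections 2.4 and 5.1 likewise limit the 12-month POP-Q and clinical findings to randomised women. The purpose of the review is "to evaluate the results of surgery and identify problems or a need for other treatment", and in some sites "this amounts to more postoperative surveillance than is available routinely in the NHS". Appendix IV confirms its use: "Randomised women were examined 12 months after surgery to identify treatment success and adverse effects".

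Two places disagree. The Summary in Plain English says women who decline randomisation "will be examined and will complete the questionnaires in the same way as the randomised groups", and section 2.7.1 says the non-randomised women are followed up just as the randomised women are.

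**The concern.** The two groups share their questionnaires but not the examination. A mesh exposure that causes no symptoms can be found in a randomised woman at month 12 and go unrecorded in a cohort woman with the same finding. If the trial analysis is then repeated on the cohort and the two effects are compared, part of any difference reflects how events were found rather than what the operations did.

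Three kinds of outcome are affected in different ways:

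- **Mesh-specific events found by examination:** under-detected in the cohort.
- **Post-operative POP-Q outcomes:** absent in the cohort, so neither replication nor comparison is possible.
- **Re-treatment after month 12:** possibly different in fact, because the review can itself lead to treatment. That would be a difference in care, not in the effect of the operation.

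At stake is the use made of the cohort. Section 8.5.1 offers it as extra information on safety and efficacy, and section 1.2 lists generalisability to the NHS as an objective. A smaller excess of complications after mesh in the cohort could be read as reassurance about mesh in ordinary practice.

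**Working it through.** The plan gives no figure to reproduce on this point, so the check asks when unequal detection alters a treatment effect and when it only lowers event rates.

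**Inputs**
- Binary outcomes are reported as odds ratios (SAP, General Methods).
- Erosion after non-absorbable synthetic mesh: 10% (protocol Appendix I, 1.2.2).
- Reoperation: 25% after standard repair, with a 10-point difference, so 15% v 25% (Appendix IV). This is a 14-year planning figure, used only to show the mechanism.
- *s*, the share of events found without the examination: not in the documents. Assumed range 0.4 to 1.0.
- Other complications: 5% in both arms, found equally in trial and cohort (assumption; 10% as a check).
- Erosion after standard repair: zero (assumption).

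**Step 1: event in both arms, equally under-detected**

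Observed rate = *s* × true rate.
- *s* = 1: 15% v 25%. RR = 0.600; OR = (0.15/0.85)/(0.25/0.75) = 0.529.
- *s* = 0.5: 7.5% v 12.5%. RR = 0.600; OR = (0.075/0.925)/(0.125/0.875) = 0.568.

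The rates halve, the RR is unchanged and the OR moves by about 7%. At *s* = 0.9 the OR is 0.538, a move of about 1.5%. A shortfall shared by both arms does little to the treatment effect.

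**Step 2: composite containing a mesh-only event**

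Rate after mesh = 1 − (1 − 0.05)(1 − 0.10*s*). Rate after standard repair = 5%, odds 0.05/0.95 = 0.0526.

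| *s* | Rate after mesh | Odds | OR v standard |
|---|---|---|---|
| 1.0 | 14.5% | 0.1696 | 3.22 |
| 0.6 | 10.7% | 0.1198 | 2.28 |
| 0.4 | 8.8% | 0.0965 | 1.83 |

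The true rates are the same in every row. With 10% other complications instead of 5%, the ORs are 2.11, 1.64 and 1.42.

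The first row assumes that the trial finds every erosion. In the pilot, 88% attended the outpatient review (section 2.4). Taking trial detection as *s* + 0.88(1 − *s*) gives 0.952 at *s* = 0.6 and 0.928 at *s* = 0.4. The trial OR is then 3.10 or 3.05, so the gap from 2.28 or 1.83 narrows only slightly.

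**Step 3: erosion as a single outcome**

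With no standard-repair events there is no ordinary odds ratio, so only raw rates can be set side by side. A true 10% appears as 6% in the cohort at *s* = 0.6 and 4% at *s* = 0.4, a gap of 4 to 6 points against full detection.

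**Step 4: timing of the shared records check**

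The HES/ISD check comes about 24 months after the last recruit (section 5.2). The 12-month analysis is due one year after recruitment closes (SAP, Timing of analyses). The check can inform the final analysis but not the 12-month one.

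**The case against.** A reader might infer that complications and re-treatment will look rarer in the cohort simply because nobody looked. The documents do not support that. Section 5.1 lists complications, need for further treatment, and treatment received or planned at 6, 12 and 24 months, with no limit to randomised women. Section 5.2 adds a central check of operations, diagnoses and admissions, and section 4.2 asks GPs to notify events. Surgery performed should reach the data in both groups, so a lower re-treatment rate in the cohort may be real.

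Other points also stand. Lower event rates are not the same as different treatment effects, as step 1 shows. The review exceeds routine care only in some sites, so some cohort women may be examined anyway, which would bring *s* closer to 1. Section 2.1 places in the cohort women whose gynaecologist thought one operation more appropriate, so case mix could move complications either way. Nor can the problem be scaled to all 1583 cohort women: some had no mesh, some had neither an anterior nor a posterior repair, and the number with mesh is not given.

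These arguments narrow the point but do not remove it. Questionnaires record what a woman knows about, not a silent exposure. An exploratory label does not correct a systematic difference in detection.

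**Conclusion.** The point holds for a limited set of outcomes. As written, the plan replicates and compares every outcome although one source of events exists only in the trials. The resulting bias in the treatment effect falls on mesh-specific events found by examination and on composites that contain them. The likely direction is that mesh looks safer in the cohort than in the trials; case mix means this is not certain.

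The size depends on a detection share that the documents do not give. Under the stated assumptions, a composite OR of 3.22 falls to 2.28 or 1.83 at 60% or 40% detection; at detection near 100% the problem is negligible. Post-operative POP-Q in the cohort is missing rather than biased downwards. Re-treatment after month 12 is a matter of possible differential care.

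POP-SS at 12 months, the other questionnaire outcomes and all randomised comparisons are untouched. Since the affected analyses are exploratory, this should be corrected before the cohort results are interpreted, but it does not threaten the main conclusions.

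**What to change.** In protocol section 6.3 and in the SAP:

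1. Base any replication, pooling or trial-versus-cohort comparison of complications and re-treatment on sources that both groups share: the 6-, 12- and 24-month questionnaires, and HES/ISD once available. Apply the same sources and the same cut-off in time from surgery to randomised and cohort women.
2. Leave out of these comparisons any event recorded only on the 12-month clinical form. Keep such events in the randomised analyses.
3. State that post-operative POP-Q outcomes are not compared with the cohort.
4. Add a sensitivity analysis limited to events before 12 months from surgery. Shared sources alone do not remove treatment prompted by the review, or problems that a woman reports because the review told her of them.
5. Present later re-treatment descriptively, with the caveat that the review may have prompted it.
6. Reconcile the Summary in Plain English and section 2.7.1 with sections 2.2 and 5.1 on whether cohort women are examined.

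With identical sources, *s* is the same in both groups and the detection artefact in step 2 disappears. The cost is SAP wording, keeping the source of each event in the analysis dataset, and fewer events in an exploratory comparison. No new data collection is needed.
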